## **Reporting Serious Adverse Events**

The Investigator must report any SAEs to the CRO within 24 hours of becoming aware of the event.

When calling to report an SAE, state that you are reporting an SAE and give the Investigator's name, your name, the telephone number where you can be reached, and the protocol number and title.

The Investigator and the Sponsor (or Sponsor's designated agent) will review each SAE report and the Sponsor/CRO will evaluate the seriousness and the causal relationship of the event to study treatment. In addition, the Sponsor (or Sponsor's designated agent) will evaluate the expectedness according to the reference documents (Investigator's Brochure or US product labeling for atomoxetine or oxybutynin). Based on the Investigator and Sponsor's assessment of the event, a decision will be made concerning the need for further action.

# 9.4 Appendix 4: Contraceptive Guidance and Collection of Pregnancy Information

## **Definitions**

## **WOCBP**

A woman is considered fertile following menarche and until becoming post-menopausal unless permanently sterile (see below).

Women in the following categories are not considered WOCBP:

- 1. Premenarchal
- 2. Premenopausal female with one of the following:
  - Documented hysterectomy
  - Documented bilateral salpingectomy
  - Documented bilateral oophorectomy

NOTE: Documentation can come from the site personnel's review of the participant's medical records, medical examination, or medical history interview.

## 3. Post-menopausal female

- A post-menopausal state is defined as no menses for 12 months without an alternative medical cause. A high follicle-stimulating hormone (FSH) level in the post-menopausal range may be used to confirm a post-menopausal state in women not using hormonal contraception or hormonal replacement therapy (HRT). However, in the absence of 12 months of amenorrhea, a single FSH measurement is insufficient.
- Females on HRT and whose menopausal status is in doubt will be required to use one of the non-estrogen hormonal highly effective contraception methods if they wish to continue their HRT during the study. Otherwise, they must discontinue HRT to allow confirmation of post-menopausal status before study enrollment.

# **Contraception Guidance:**

## **Male Participants:**

Male participants with female partners of childbearing potential are eligible to participate if the agree to ONE of the following during the protocol-defined time frame:

- Are abstinent from penile-vaginal intercourse as their usual and preferred lifestyle (abstinent on a long-term and persistent basis) and agree to remain abstinent.
- Agree to use a contraceptive method with a failure rate of <1% per year as described in the table below when having penile-vaginal intercourse with a WOCBP who is not currently pregnant.

In addition, male participants must refrain from donating sperm for the duration of the study and for 3 months after the last dose of study treatment.

Male participants with a pregnant or breastfeeding partner must agree to remain abstinent from penile-vaginal intercourse or to use a male condom during each episode of penile penetration during the protocol-defined time frame.

# **Female Participants**

Female participants of childbearing potential are eligible to participate if they agree to use a highly effective method of contraception consistently and correctly as described in the table below.

# Highly Effective Contraceptive Methods That Are User Dependent

Failure rate of <1% per year when used consistently and correctly.

Combined (estrogen- and progestin-containing) hormonal contraception associated with inhibition of ovulation

- Oral
- Intravaginal
- Transdermal

Progestogen-only hormonal contraception associated with inhibition of ovulation

- Oral
- Injectable

# Highly Effective Contraceptive Methods That Are User Independent

Implantable progestogen-only hormonal contraception associated with inhibition of ovulation

- IUD
- Intrauterine hormone-releasing system (IUS)
- Bilateral tubal occlusion

## Vasectomized partner

A vasectomized partner is a highly effective contraception method provided that the partner is the sole male sexual partner of the WOCBP and the absence of sperm has been confirmed. If not, an additional highly effective method of contraception should be used.

## Sexual abstinence

Sexual abstinence is considered a highly effective method only if defined as refraining from heterosexual intercourse during the entire period of risk associated with the study treatment. The reliability of sexual abstinence needs to be evaluated in relation to the duration of the study and the preferred and usual lifestyle of the participant.

## NOTES:

1 Typical use failure rates may differ from those when used consistently and correctly. Use should be consistent with local regulations regarding the use of contraceptive methods for participants participating in clinical studies.

# **Pregnancy Testing**

- WOCBP should only be included after a confirmed menstrual period and a negative highly sensitive serum pregnancy test.
- An additional serum pregnancy testing should be performed at Visit 5 (EOS).

• Pregnancy testing will be performed whenever a menstrual cycle is missed or when pregnancy is otherwise suspected.

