## 1.2 Schedule of Activities (SoA)

 Table 1
 Schedule of Activities

	Screening		4-Way Crossover Period Visit 3-6						End of Study Evaluation 		
Procedures	Daytime V1	PSG V2	PSG V3	Wash- out 	PSG V4	Wash- out	PSG V5	Wash- out	PSG V6	Wash- out	
Trial Day (Visit Window)	Up to 4 w	veeks				Up to 8	weeks				2 weeks post V6 ± 3 days
Informed consent	X										
Non-PSG enrollment criteria	X										
Demography	X										
ESS	X										
Physical exam	X										
Medical history	X										
Clinical laboratory test	X										
Pregnancy test 	X										
12 Lead ECG	X										
PSG Exam		$X^4$	X		X		X		X		
Randomization 			X								
Administration of study treatment 			X		X		X		X		
DSST 			X		X		X		X		
Vital signs 	X	X	X		X		X		X		
AE/SAE monitoring			X	X	X	X	X	X	X	X	X
Prior/concomitant medication monitoring	X	X	X	X	X	X	X	X	X	X	X

Abbreviations: AE = adverse event; DSST = Digit Symbol Substitution Test; ECG = electrocardiogram; ESS = Epworth Sleepiness Scale; PSG = polysomnography; SAE = serious adverse event; WOCBP = women of childbearing potential.

<sup>1 Can be conducted remotely. For patients enrolling in Study APC-003-OLE, can be conducted concurrently with first visit of Study APC-003-OLE.

<sup>2 Each washout period is a minimum of 7 days

<sup>3 WOCBP only

<sup>4 A PSG conducted by the study site within 6 months that meets PSG enrollment criteria can take the place of a screening PSG and V2

<sup>5 Randomization occurs when participant meets enrollment criteria up to the time of the first crossover period

<sup>6 Study medication administered immediately before lights out

<sup>7 Administer at similar time after awakening after each crossover PSG, approximately 1 hour after awakening

<sup>8 Vital signs include the following: seated blood pressure, pulse, respiratory rate; vital signs on PSG nights taken after admission to PSG lab

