## 7 Study Assessments and Procedures

- Study procedures and their timing are summarized in the SoA.
- Adherence to the study design requirements, including those specified in the SoA, is essential and required for study conduct.
- All screening evaluations must be completed and reviewed to confirm that potential
  participants meet all eligibility criteria. The Investigator will maintain a screening log to
  record details of all participants screened and to confirm eligibility or record reasons for
  screening failure, as applicable.

- The maximum amount of blood collected from each participant over the duration of the study, excluding any extra assessments that may be required for safety or technical issues, will not exceed approximately 50 mL.
- Repeat or unscheduled samples may be taken for safety reasons or for technical issues with the samples, as per the Investigator or designee's discretion.

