**Table 2: Protocol-Required Safety Laboratory Assessments** 

Laboratory Assessments	Parameters		
Hematology	Hematocrit Hemoglobin Platelet Count RBC Count	RBC Indices (MCV, WBC count with Differential MCH, MCHC)	
Serum Chemistry	Albumin BUN Creatinine Potassium Sodium Bilirubin Total Protein Uric acid	ALT AST Alkaline phosphatase Calcium Glucose Total cholesterol Chloride Bicarbonate	
Routine Urinalysis	Specific gravity, bilirubin, color, appearance, leukocyte esterase, nitrite, pH, protein (albumin), glucose, ketones, occult blood, urobilinogen Microscopic examination (if positive protein, leukocyte esterase, blood or nitrite)		
Other Tests	
 
HbA1c (Screening Visit only)
 
Serum hCG pregnancy test at screening. Additional testing may be performed if needed in WOCBP.
 
Urine test of drugs of abuse (marijuana, cocaine, amphetamine, methamphetamine, opiates, phencyclidine)
 
		

Abbreviations: ALT = alanine aminotransferase; AST = aspartate aminotransferase; BUN = blood urea nitrogen; HbA1c = hemoglobin A1c (glycated hemoglobin); hCG = human chorionic gonadotropin; RBC = red blood cell count; WBC= white blood cell; WOCBP = women of childbearing potential.

Investigators must document their review of each laboratory safety report.

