# 9.5 Appendix 5: List of Abbreviations

AHI apnea-hypopnea index

AE adverse event

Bang Body mass index, Age, Neck circumference, and Gender criteria

BMI body mass index

CFR Code of Federal Regulations

CNS central nervous system

CPAP continuous positive air pressure

CYP2D6 cytochrome P450 2D6 CYP3A4 cytochrome P450 3A4

DSM-5 Diagnostic and Statistical Manual of Mental Disorders, 5th edition

ECG electrocardiogram
EEG electroencephalogram

eCRF electronic case report form(s)

EDC electronic data capture

EOS end of study

FSH follicle-stimulating hormone

GCP Good Clinical Practice

HB Hypoxic burden

HRT hormone replacement therapy

ICF informed consent form

ICH International Conference on Harmonisation

IEC Independent Ethics Committee

IND Investigational New Drug

IPSS International Prostate Symptom Score

IRB Institutional Review Board

IRT Interactive Response Technology

OSA obstructive sleep apnea

OTC over-the-counter

MAOI monoamine oxidase inhibitor NREM non-rapid eye movement

PK pharmacokinetic(s)
PSG polysomnography

QHS 1 dose every night at bedtime

REM rapid eye movement

SAE serious adverse eventSAP Statistical Analysis PlanSoA Schedule of Activities

STOP Snoring, Tiredness, Observed apnea, and Blood pressure criteria

SUSAR suspected unexpected serious adverse reaction

ULN upper limit of normal

US United States

WOCBP woman of childbearing potential

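### Appendix 4 schedules a serum pregnancy test at Visit 5 (EOS), but no visit carries both labels, and the Schedule of Activities marks no pregnancy test after screening

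*Protocol*

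**What the plan says.** Four places in the protocol bear on when WOCBP are tested for pregnancy.

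- **Appendix 4 (Section 9.4), Pregnancy Testing.** Besides the negative serum test needed for inclusion: "An additional serum pregnancy testing should be performed at Visit 5 (EOS"). The next item adds: "Pregnancy testing will be performed whenever a menstrual cycle is missed or when pregnancy is otherwise suspected".
- **Appendix 5 (Section 9.5).** The abbreviation is defined: "EOS end of study".
- **SoA (Section 1.2, Table 1).** The crossover runs from V3 to V6. The End of Study Evaluation has its own unnumbered column, timed "2 weeks post V6 ± 3 days", with the footnote "Can be conducted remotely". The pregnancy-test row has one mark, at V1.
- **Appendix 2 (Section 9.2), Table 2.** "Serum hCG pregnancy test at screening. Additional testing may be performed if needed in WOCBP".

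Section 7 tells sites where to look for timing: "Study procedures and their timing are summarized in the SoA". Section 7.2.4 also refers them to the SoA for the timing and frequency of laboratory tests. SAP Appendix A reprints the SoA.

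**The concern.** The Appendix 4 sentence is an operative safety instruction, and it is the only place where the protocol schedules a pregnancy test after screening. Its visit number and its abbreviation point to different occasions, and the table that sites plan from shows neither.

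The stakes are practical. A test at V5 comes before the last dose and can say nothing about the time after it. A site that builds its visit plan from the SoA would leave the test out. A positive result starts the 24-hour report to the sponsor and the outcome follow-up described in Appendix 4, and Section 7.3.5 requires pregnancies to be collected until at least 5 terminal half-lives after the last dose. Sites should therefore not have to guess when the test is due. Nothing in the efficacy analysis depends on it.

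**Working it through.** There is no figure in the plan to reproduce. The check sets the sections side by side, with simple date arithmetic.

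**Inputs, all from the protocol**
- Visit order (SoA): V1 daytime screening, V2 screening PSG, V3 to V6 crossover nights with dosing, then End of Study.
- Gap between dosing nights (SoA footnote 2): "Each washout period is a minimum of 7 days".
- End of Study timing (SoA): 2 weeks after V6, ±3 days.
- Meaning of EOS (Appendix 5): end of study.

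**Step 1: where V5 falls.** The dosing nights are V3, V4, V5 and V6, so V5 is the third of four. The V6 dose follows at least 7 days later.

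**Step 2: where End of Study falls.** 14 − 3 = 11 days to 14 + 3 = 17 days after V6.

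**Step 3: distance between the two labels.** At least 7 + 11 = 18 days, with the V6 dose in between. They cannot be the same occasion.

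**Step 4: what the SoA schedules.** In the protocol's table the AE/SAE row has nine marks, running from V3 through the four washouts and the other PSG nights to the End of Study column, so the columns are intact. The pregnancy-test row has its single mark at V1 and is blank at V5 and at End of Study. Inclusion criterion 5 and Table 2 also place the required test at screening. The check does not rely on the SAP's copy of the table.

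**Step 5: what each reading gives**

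| Reading | Test after screening | Relation to the V6 dose |
|---|---|---|
| Appendix 4 by visit number | V5 | at least 7 days before |
| Appendix 4 by the abbreviation EOS | End of Study | 11 to 17 days after |
| Site planning from the SoA | none planned | not applicable |

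Table 2 does not settle the choice. It makes later tests conditional on need, whereas Appendix 4 states its extra test as a scheduled one. The instruction to test on a missed cycle or on suspicion does not settle it either, because it is a separate item.

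**Step 6: can the End of Study test be done as written?** If the evaluation is in person, yes, and every section is then satisfied. If it is remote, a serum test still needs a blood draw, and no section says where. Appendix 2 sends the Table 2 tests to the central laboratory.

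**The case against.** The best defence is that the meaning is clear enough. EOS is defined, an in-person draw at End of Study satisfies every section, and the SoA only summarises procedures. Section 9.1.9 says the protocol is to be followed exactly, so Appendix 4 binds even where the SoA is silent. Footnote 1 also lets End of Study coincide with the first visit of the open-label extension. Other safeguards remain: a negative screening test, highly effective contraception until one week after the last dose, testing on a missed cycle or suspicion, and withdrawal of any participant who becomes pregnant. All of this stands, and it keeps the point minor. It does not remove the wrong pairing of labels, the missing SoA mark or the gap for remote evaluations.

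It can also be said that End of Study is not the proven intent. A test before the V5 or V6 dose could prevent a dose to a pregnant participant; an End of Study test could not. That is fair. The sponsor should confirm the visit, and the text needs correcting whichever visit was meant.

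A reader might infer three stronger things that the documents do not support:

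- **That no woman would be tested after dosing begins.** This treats Appendix 4 as absent. A site following the whole protocol has a later test; what is unclear is when.
- **That a ceiling on missed pregnancies follows from the contraceptive failure rate of under 1% per year.** That rate does not govern screening, before contraception is required, or the days after the requirement ends. Appendix 4 notes that typical-use rates may differ, and the number of WOCBP is not given.
- **That an End of Study test would detect any pregnancy arising around the last dose.** The documents say nothing about how soon after conception the test turns positive.

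**Conclusion.** The inconsistency is real and minor. Appendix 4 gives its scheduled pregnancy test a label that matches no visit: the number points to the third dosing night, and the abbreviation to an evaluation at least 18 days later. The SoA marks neither. By the visit number, the test falls at least 7 days before the last dose; by the SoA, it would not be planned.

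The conclusion rests on the protocol's own visit numbering, the minimum 7-day washout and the stated End of Study window. That End of Study is the intended visit is likely, from the definition of EOS, but it is an inference. No count of exposures or pregnancies is attached, because the documents give neither draw times within a visit nor the number of WOCBP. Efficacy, power and type I error are unaffected.

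**What to change.** - **Appendix 4, Pregnancy Testing:** replace the label Visit 5 (EOS) with the End of Study evaluation. If the sponsor meant another visit, name that one and carry it through the changes below.
- **SoA (protocol Section 1.2 and SAP Appendix A):** mark a serum pregnancy test for WOCBP in the matching column.
- **Appendix 2, Table 2:** list the serum hCG test for WOCBP at screening and at End of Study, with further tests as needed.
- **SoA footnote 1:** state that a WOCBP whose End of Study evaluation is remote still needs a blood draw at the site or locally. Since Table 2 tests go to the central laboratory, say whether a local result is accepted.

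The cost is a few words in each place and one serum test per WOCBP, which Appendix 4 already requests. The one small downside is the draw for a WOCBP whose evaluation would otherwise have been wholly remote. Dosing, other participants' visits and the analysis do not change.

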# **Collection of Pregnancy Information:**

# Female participants who become pregnant

- The Investigator will collect pregnancy information on any female participant who becomes pregnant while participating in this study. Information will be recorded on the appropriate form and submitted to the Sponsor within 24 hours of learning of a participant's pregnancy. The participant will be followed to determine the outcome of the pregnancy. The Investigator will collect any follow up information on the participant and the neonate and the information will be forwarded to the Sponsor. Generally, follow up will not be required for longer than 6 to 8 weeks beyond the estimated delivery date. Any termination of the pregnancy will be reported, regardless of fetal state (presence or absence of anomalies) or indication for the procedure.
- While pregnancy itself is not considered to be an AE or SAE, any pregnancy complication or elective termination of a pregnancy will be reported as an AE or SAE. A spontaneous abortion is always considered to be an SAE and will be reported as such. Any post-study pregnancy-related SAE considered reasonably related to the study treatment by the Investigator will be reported to the Sponsor. While the Investigator is not obligated to actively seek this information in former study participants, he or she may learn of an SAE through spontaneous reporting.
- Any female participant who becomes pregnant while participating in the study will be withdrawn from the study.

# 9.5 Appendix 5: List of Abbreviations

AHI apnea-hypopnea index

AE adverse event

Bang Body mass index, Age, Neck circumference, and Gender criteria

BMI body mass index

CFR Code of Federal Regulations

CNS central nervous system

CPAP continuous positive air pressure

CYP2D6 cytochrome P450 2D6 CYP3A4 cytochrome P450 3A4

DSM-5 Diagnostic and Statistical Manual of Mental Disorders, 5th edition

ECG electrocardiogram
EEG electroencephalogram

eCRF electronic case report form(s)

EDC electronic data capture

EOS end of study

FSH follicle-stimulating hormone

GCP Good Clinical Practice

HB Hypoxic burden

HRT hormone replacement therapy

ICF informed consent form

ICH International Conference on Harmonisation

IEC Independent Ethics Committee

IND Investigational New Drug

IPSS International Prostate Symptom Score

IRB Institutional Review Board

IRT Interactive Response Technology

OSA obstructive sleep apnea

OTC over-the-counter

MAOI monoamine oxidase inhibitor NREM non-rapid eye movement

PK pharmacokinetic(s)
PSG polysomnography

QHS 1 dose every night at bedtime

REM rapid eye movement

SAE serious adverse eventSAP Statistical Analysis PlanSoA Schedule of Activities

STOP Snoring, Tiredness, Observed apnea, and Blood pressure criteria

SUSAR suspected unexpected serious adverse reaction

ULN upper limit of normal

US United States

WOCBP woman of childbearing potential

AE	adverse event
ATC	anatomical, therapeutic, and chemical
CI	confidence interval
CRO	contract research organization
CSR	clinical study report
DSST	digit symbol substitution test
ECG	electrocardiogram
eCRF	electronic case report form(s)
EDC	electronic data capture
HB	hypoxic burden
HR	heart rate
ICF	informed consent form
LS	least square
MedDRA	medical dictionary for regulatory activities
mITT	modified intent to treat
NAW	number of awakenings
NREM	non-rapid eye movement
ODI	oxygen desaturation index
OSA	obstructive sleep apnea
PP	per protocol
PSG	polysomnography
PT	preferred term
REM	rapid eye movement

Abbreviation	Definition
SAE	serious adverse event
SaO ₂	oxygen saturation
SAP	statistical analysis plan
SD	standard deviation
SE	sleep efficiency
SOC	system organ class
SOL	sleep onset latency
TEAE	treatment-emergent adverse event
TST	total sleep time
WASO	wake after sleep onset
WHO	world health organization

1. INTRODUCTION

This statistical analysis plan (SAP) is based on the Protocol # APC-003 Version 2.0, dated 06 January 2021, titled “Phase 2 Randomized Double-Blind Placebo-Controlled 4-Period Single-Dose Crossover Factorial Study to Evaluate the Contribution of the Individual Drug Components to the Efficacy of the Combination of Atomoxetine and R-oxybutynin in Obstructive Sleep Apnea.” AD109 is a new fixed-dose combination of atomoxetine and R-oxybutynin being developed for obstructive sleep apnea (OSA). Study APC-003 is designed to compare the efficacy of AD109 to placebo and the individual components of AD109, atomoxetine and R-oxybutynin, in OSA.

This document details the statistical methods planned to perform the final analyses of this study.

2. OBJECTIVES AND ENDPOINTS

2.1. Objectives

2.1.1. Primary Objective

The primary objective is to evaluate the efficacy of AD109 compared to placebo as measured by the 4% definition of hypoxic burden (HB).

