#### **Rationale:**

Previous studies conducted by the sponsor (under IND 136752) and academic investigators indicate that the combination drug composed of atomoxetine and oxybutynin (designated AD036) is effective for the treatment of obstructive sleep apnea (OSA). Oxybutynin is a racemic mixture of R and S enantiomers. Oxybutynin is approved in the U.S. for overactive bladder. Efficacy of oxybutynin in overactive bladder may result both from antimuscarinic effects and smooth muscle spasmolytic effects. The contribution to efficacy of oxybutynin in OSA is believed to be related to the antimuscarinic effects, whereas spasmolytic effects may lead to effects on the bladder that are undesirable in typical OSA patients. The R-enantiomer of oxybutynin has been shown to confer the antimuscarinic effect of oxybutynin, whereas the spasmolytic effects (and other effects on calcium channel antagonism and local anesthetic effects) are non-stereoselective properties of both the enantiomers. Apnimed therefore believes that the combination of the R-enantiomer of oxybutynin with atomoxetine, designated AD109, may have an improved safety and efficacy profile in OSA compared to the combination with the racemate of oxybutynin.

This factorial study is designed to demonstrate that both atomoxetine and R-oxybutynin contribute to the efficacy of AD109 in OSA, and thus to fulfill FDA requirements for approval of combination drugs under 21 CFR Subpart B Section 300.50 Fixed-combination prescription drugs for humans.

6 January 2021 6 of 50 V2.0

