#### **Overall Design:**

Study APC-003 is a randomized, double blind, placebo-controlled, 4-period, single-dose crossover factorial study in patients with OSA. A screening visit and polysomnographic (PSG) exam will be conducted to establish that each participant meets study enrollment criteria. Each participant will then receive a single dose of each of the following during 4 overnight PSG exams, each separated by a one week washout period:

- Atomoxetine 75 mg + R-oxybutynin 2.5 mg (AD109)
- Atomoxetine 75 mg
- R-oxybutynin 2.5 mg
- Placebo

The primary hypothesis of the crossover study is that AD109 is superior to each of the other 3 arms, on the endpoint of Hypoxic Burden (HB), a measure of the depth and duration of the ventilatory disturbance in OSA.

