## 3 Endpoints

	Endpoints
Primary	Change in Hypoxic Burden (HB) 4%, (scored in reference to AHI 4%), AD109     vs. other 3 study treatments
Secondary	
 
Change in Apnea Hypopnea Index (AHI) 4%
 
Change in Oxygen Desaturation Index (ODI)
 
Total time with SaO2 <90%, PSG nights
 
Proportion of participants with ≥50% reduction, AHI, HB and ODI
 

Exploratory	
 
PSG sleep and arousal parameters
 
PSG respiratory parameters
 

Safety Endpoints	
 
Physical exam, vital signs, clinical laboratory assessment
 
Spontaneous adverse events, including the post-dosing period
 
DSST
 
PSG parameters: heart rate, ECG, EEG, oximetry
 

Abbreviations: AHI = apnea-hypopnea index; DSST = Digit Symbol Substitution Test; ECG = electrocardiogram; EEG = electroencephalogram; HB = Hypoxic Burden; ODI = Oxygen Desaturation Index; OSA = obstructive sleep apnea; PSG = polysomnography; SaO2 = oxygen saturation.

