#### 8 Statistical Considerations

## **8.1** Sample Size Determination

A total of 58 patients will enter the 4-treatment crossover study. The study will have 80% power to detect a treatment difference at a two-sided 0.05 significance level, if the true difference between treatments on HB is at least -3.7 %min/h. This assumes that the within-subject standard deviation is 9, estimated from Study APN-006, and that the discontinuation rate is less than 20%.

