# 9.1.9 Protocol Approval and Amendment

Before the start of the study, the study protocol and/or other relevant documents will be approved by the IEC/IRB/Competent Authorities, in accordance with local legal requirements. The Sponsor must ensure that all ethical and legal requirements have been met before the first participant is enrolled in the study.

This protocol is to be followed exactly. To alter the protocol, amendments must be written, receive approval from the appropriate personnel, and receive IRB/IEC/Competent Authority approval prior to implementation (if appropriate). Following approval, the protocol amendment(s) will be submitted to the US Investigational New Drug (IND) under which the study is being conducted.

Administrative changes (not affecting the participant benefit/risk ratio) may be made without the need for a formal amendment. All amendments will be distributed to all protocol recipients, with appropriate instructions.

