2.1.2. Secondary Objectives

The secondary objectives include:

- To evaluate the efficacy of AD109 compared to R-oxybutynin alone as measured by HB(4%)
- To evaluate the efficacy of AD109 compared to atomoxetine alone as measured by HB(4%)
- To evaluate the efficacy of AD109 compared to the other 3 study treatments as measured by the 4% definition for hypopneas (AHI).
- To evaluate the efficacy of AD109 compared to the other 3 study treatments as measured by the 4% definition of oxygen desaturation index (ODI).
- To evaluate the efficacy of AD109 compared to the other 3 study treatments as measured by total time with $\text{SaO}_2 < 90\%$.
- To evaluate the efficacy of AD109 compared to the other 3 study treatments on the proportion of participants with $\geq 50\%$ reduction in AHI, HB and ODI.

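### The SAP makes only AD109 versus placebo primary on HB(4%), while the protocol's primary hypothesis needs AD109 to beat all three other arms; the stated 80% power is for one contrast only

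*SAP*

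**What the plan says.** **Protocol, Version 2.0.** The synopsis (Rationale) gives the purpose: "This factorial study is designed to demonstrate that both atomoxetine and R-oxybutynin contribute to the efficacy of AD109 in OSA". Overall Design gives the hypothesis: "The primary hypothesis of the crossover study is that AD109 is superior to each of the other 3 arms", on HB. Section 3 lists one primary endpoint, change in HB 4%, with AD109 compared "vs. other 3 study treatments". Section 9.1.9 adds: "This protocol is to be followed exactly. To alter the protocol, amendments must be written", with an exception for administrative changes.

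**SAP.** The Introduction says: "This statistical analysis plan (SAP) is based on the Protocol # APC-003 Version 2.0, dated 06 January 2021". Section 2.1.1 then says: "The primary objective is to evaluate the efficacy of AD109 compared to placebo as measured by the 4% definition of hypoxic burden (HB"). Section 2.2.1 names the single contrast with placebo, on log10(HB[4%]+1). Sections 2.1.2 and 2.2.2 list AD109 versus R-oxybutynin and AD109 versus atomoxetine on HB(4%) as secondary. Section 4.5 tests placebo, then R-oxybutynin, then atomoxetine in fixed sequence, each at two-sided 0.05. Section 6.1 analyses all three contrasts in one model.

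**Power.** Protocol 8.1 and SAP 9 give the same statement: 58 participants, 80% power at two-sided 0.05 for a true HB difference of -3.7 %min/h, and discontinuation under 20%. On variability the protocol says: "This assumes that the within-subject standard deviation is 9, estimated from Study APN-006".

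**The concern.** The protocol's primary question is whether each component contributes. A comparison with placebo cannot answer it, because AD109 could beat placebo through one component alone. The SAP nevertheless makes that comparison the whole of its primary objective. It cites the same protocol version, so this is not a version mismatch, and no supplied text acknowledges or justifies the change. The SAP's commitment to document changes in the study report (section 4) covers analyses not included in the SAP, so it would not pick this up.

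The same data could therefore be reported as meeting the primary objective (SAP) and as not showing the primary hypothesis (protocol). A reader of the power statement could also take 80% as the chance of showing what the protocol calls primary, although it refers to one treatment difference.

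**Working it through.** **1. Side by side.**

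| HB(4%) contrast | Protocol (1.1, 3) | SAP (2.1, 2.2) | Step in SAP 4.5 |
|---|---|---|---|
| AD109 vs placebo | primary | primary | 1 |
| AD109 vs R-oxybutynin | primary | secondary | 2 |
| AD109 vs atomoxetine | primary | secondary | 3 |

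In a fixed sequence, reaching and winning step 3 means winning all three tests at 0.05. That is the same rejection rule as requiring all three with no alpha split.

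**2. Reproducing the 80%.** Inputs from protocol 8.1: difference 3.7, SD 9, N = 58, dropout limit 20%. Completers at the limit: 58 × 0.8 = 46.4, taken as 46.

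- Noncentrality = difference × √n / SD of the paired difference.
- If 9 is the SD of the paired difference: 3.7 × √46 / 9 = 2.788. Normal approximation: Φ(2.788 − 1.960) = 79.6%. Paired t: 77.9%.
- Required n = (9 × (1.960 + 0.842) / 3.7)² = 46.4, so 47. Then 47 / 0.8 = 58.75, so 59, against the stated 58.
- If 9 is literally the within-subject SD, the SD of the difference is 9√2 = 12.73. Noncentrality is 1.972 and power is 50.5% (normal) or 48.8% (paired t).

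The 80% is therefore reproduced for **one** contrast, and only on the first reading of the SD.

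**3. Power for all three.** Assumptions not in the documents: a true difference of 3.7 from each component; a placebo difference of 3.7, or 1.5 to 2 times that; independent, equal within-participant errors. The contrasts share the AD109 arm, so their correlation is σ² / 2σ² = 0.5. Method: simulation of 200,000 trials per row, paired t on completers, raw HB.

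| SD of difference | n | Placebo difference | Placebo won | All three won | Placebo won, not all three |
|---|---|---|---|---|---|
| 9 | 46 | 3.7 | 78% | 58% | 20% |
| 9 | 46 | 1.5–2× | 98–100% | 65–66% | 33–34% |
| 9 | 58 | 3.7 | 87% | 72% | 14% |
| 9 | 58 | 1.5–2× | about 100% | 78% | 21–22% |
| 12.73 | 46 | 3.7 | 49% | 24% | 25% |
| 12.73 | 46 | 1.5–2× | 82–97% | 31–32% | 52–65% |
| 12.73 | 58 | 3.7 | 58% | 33% | 25% |
| 12.73 | 58 | 1.5–2× | 90–99% | 41–42% | 49–57% |

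The n = 46 rows are the dropout limit and the n = 58 rows assume no dropout; the plan allows anything between. Within each n and SD, the spread comes from the assumed placebo effect.

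**4. Error check.** If AD109 beats placebo and one component by 3.7 but the other component contrast is zero, all three are won in about 2.4% of trials (n = 46, SD of difference 9). This is below the 2.5% in the favourable tail of one two-sided 0.05 test.

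**The case against.** The strongest reply is that only labels differ. All three HB contrasts are tested at full alpha, ahead of AHI and ODI, and reported together from one model. A confirmatory statement about both components already needs three wins. No estimate, p-value or error rate would change. This stands, and it limits the point to consistency between the documents.

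It is also true that neither document states a formal success rule. Protocol section 8 gives no model, multiplicity plan or decision rule. That the primary requires all three is a reading of the hypothesis that AD109 be superior to each arm. It is the natural reading, and the section 3 endpoint supports it.

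The simulation has limits. It uses raw HB, whereas the SAP's primary is on log10(HB+1). A completers-only paired t also drops partial data that the SAP's mITT repeated-measures model would keep.

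A reader might infer three stronger points that the documents do not support:

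- **That type I error is inflated, or the component tests are lost.** SAP 4.5 rules this out.
- **That the last column of the table is a false-claim rate.** It is the chance that the two documents' primary results differ. If one component is inert, that chance is about 75% at n = 46 (SD of difference 9), but each document then answers its own question correctly.
- **That the power statement is wrong because joint power is lower.** Both documents speak of a single treatment difference and make no joint claim. If the placebo and R-oxybutynin differences were much larger (8, an assumption), joint power would return to about 80% (normal approximation, n = 46, SD of difference 9).

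**Conclusion.** The point holds as an unexplained contradiction over what is primary. The protocol's primary hypothesis covers three HB contrasts; the SAP's primary objective covers one, and that one does not address contribution of components. The contradiction depends on no calculation.

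Its size is indicative. With 9 as the SD of the paired difference and a true difference of 3.7 from each component, power for all three contrasts is about 58–66% at 46 completers and 72–78% at 58, against the stated 80% for one. The chance of beating placebo without winning all three is about 20–34% and 14–22% respectively. If 9 is literally the within-subject SD, power for all three is about 24–32% and 33–42%. All figures assume a correlation of 0.5 and raw HB. With no SD given for log10(HB+1), none describes the SAP's planned scale.

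This should be fixed, but it does not threaten the validity of the HB tests.

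**What to change.** Reconcile the documents before unblinding, in one of two ways.

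1. In SAP 2.1.1, 2.1.2, 2.2.1 and 2.2.2, make the three HB(4%) contrasts the primary family. The primary objective is met only if all three favour AD109 at two-sided 0.05, with no alpha split.
2. If the placebo-only primary is intended, amend the protocol to match, give the reason, and state in the SAP that any contribution-of-components conclusion requires all three HB steps of section 4.5.

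In either case, say in protocol 8.1 and SAP 9 that the 80% is power for a single contrast, and give the joint power for all three with its assumptions.

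**Cost.** The tests, their order and alpha stay the same. Option 1 makes the primary harder to meet and the reported power less favourable. Option 2 needs a protocol amendment.
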